## Axillary lymph node involvement at surgery

This is a binary outcome recorded as either lymph node involvement or not.

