#### Secondary

- Objective ultrasound-determined response (CR, PR) to neoadjuvant treatment
- Type of surgery
- Axillary lymph node involvement at surgery
- Complete pathological response
- Local recurrence-free survival
- Progression-free survival
- Overall survival

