## 6. PATIENT SELECTION

### 6.1 Inclusion criteria

The study population consists of postmenopausal women diagnosed with resectable breast cancer, who meet the following eligibility criteria:

- Biopsy proven, ER positive invasive breast cancer (where ER positive is defined as equivalent to an ER “Quick or Allred score” of 3 or greater)
- Tumour, measured on U/S, as greater than 2 cm in diameter
- Postmenopausal, defined as:
  - Any Age:- bilateral surgical oophorectomy
    - amenorrhea  $\geq$  5 years (any cause)

Age  $\geq$  50 yrs:- natural amenorrhea for  $\geq$  1 year

Age  $<50$  yrs: - if amenorrhea  $< 5$  years or hysterectomy without bilateral surgical oophorectomy, then FSH, LH and oestradiol must be assayed to confirm postmenopausal status

- Adequate haematological, renal and liver function, defined as a platelets of  $>100 \times 10^9/l$ , white blood cell count of  $>3 \times 10^9/l$ , creatinine  $<110$  mmol/l, AST and/or ALT  $< 1.25 \times$  upper limit of normal
- Patients must be fit to complete surgery for their breast cancer
- Written informed consent
- ECOG performance status 0,1 or 2

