### RANDOMISATION

(9:00am till 5:00pm, Monday to Friday)

☎ [name] or [name]

✉ [name]

During the randomisation procedure eligibility criteria and randomisation details will be confirmed and verification that the patient has signed the NEO-EXCEL Informed Consent Form will be requested. A unique sequential Trial Number (TNO) will be allocated. This number should be used on all Case Report Forms (CRFs) and all subsequent correspondence relating to that patient. The TNO and allocated treatment must also be recorded on the Randomisation Form, and the Form then signed and dated. The completed original Forms should be sent to the NEO-EXCEL Study Office, with copies retained at site. Confirmation of the randomised treatment allocation will be sent to the Investigator and appointed Pharmacist.

Randomisation will be stratified by tumour size (>2-5cm, >5cm), grade (I, II, III), ER Q-score (3-4, 5-6, 7-8), Her2 (-ve, +ve, not determined), and low dose aspirin use (yes, no). This information therefore must be available at randomisation. A computerised minimisation algorithm, developed by the Trials Unit, will be used to ensure that allocation of treatment to patients is balanced within these strata.

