### At Screening

- Relevant medical history including:
  - cardiac history
  - thromboembolic history
  - rheumatological history
  - other serious acute or chronic conditions
- Concomitant medication (description of other medication prescribed for more than 7 days and taken within one month of randomisation)
- ECOG performance status (Appendix 1)
- Clinical examination, including height and body weight
- Uni-dimensional tumour measurement by calipers of the greatest dimension
- Tumour assessment by ultrasound
- Base-line blood tests: full blood count; urea + creatinine + electrolytes; liver function tests
- Blood pressure measurement
- NYHA classification (see section 6.2)

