**Refer to Investigator Site File/Pharmacy File for procedure outwith office hours.**

## 14. STATISTICAL CONSIDERATIONS

### 14.1 Definition of Outcome Measures

The treatment arms will be compared in terms of the following outcome measures:

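### Nodal involvement at surgery is compared between arms, but the protocol schedules no record of axillary status before treatment, so baseline balance cannot be checked and cleared nodes look the same as nodes never involved

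*Protocol*

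**What the plan says.** Protocol section 5 lists "Axillary lymph node involvement at surgery" among the secondary outcomes. Section 14.1 opens with "The treatment arms will be compared in terms of the following outcome measures" and defines the nodal outcome in one line: "This is a binary outcome recorded as either lymph node involvement or not". The definition does not refer to status before treatment.

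The places where pre-treatment axillary status could appear are these:

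- **Eligibility (6.1, 6.2).** "The study population consists of postmenopausal women diagnosed with resectable breast cancer, who meet the following eligibility criteria". There is no nodal criterion, so node-negative and node-positive women can both enter.
- **Screening (section 9).** "Clinical examination, including height and body weight", a calliper measurement of the tumour, and "Tumour assessment by ultrasound". The axilla is not named.
- **Baseline (section 9) and Figure 1.** Clinical examination, core biopsy and research bloods; no node sampling and no clinical N stage.
- **Minimisation (section 7).** "Randomisation will be stratified by tumour size (>2-5cm, >5cm), grade (I, II, III), ER Q-score (3-4, 5-6, 7-8", and the list ends with HER2 and aspirin use. Nodal status is not a factor.

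The only other trial-specific mention of nodal positivity is in section 16, where it is a finding at definitive surgery. Appendix 4 mentions palpable lymph nodes only as general RECIST guidance.

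**The concern.** The breast lesion is measured before and after treatment and judged by its change. The axilla is judged only afterwards. A woman with clear nodes at surgery may have had involved nodes that cleared, or may never have had nodal disease, and the scheduled data cannot say which. For an outcome meant to reflect neoadjuvant treatment, that limits what a difference, or the lack of one, can mean.

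Starting nodal status should also be a strong predictor of nodal status at surgery. Without it, a chance difference between arms at entry passes unseen into the comparison. A later analysis plan cannot repair this, because it cannot adjust for a value that sites were not asked to record, and that value cannot be observed once treatment has begun.

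**Working it through.** **The plan's own figures.** Section 14.3 powers the primary outcome only. The two-proportion formula is

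power = Φ{ [ |p0 − p1|·√n − 1.96·√(2·p̄(1−p̄)) ] / √( p0(1−p0) + p1(1−p1) ) }, two-sided 5%.

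- 55% v 68%, 250 per arm: 85.0% (stated 85%).
- 55% v 64%, 500 per group: 82.7% (stated 80%; 488 per group gives 80% with continuity correction).

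Both reproduce. No rate, target difference or power is given for the nodal outcome.

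**Assumptions.** None of these comes from the protocol. Let b be the share node-positive at entry, 30-50%. Of entry-positives, 90% are still positive at surgery in one group and 80% in the other. Of entry-negatives, 15% are positive at surgery in both. Each group has 500 women (one factorial margin).

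**Step 1, unadjusted.** The proportion positive at surgery is b·q + (1−b)·0.15, with q = 0.90 or 0.80. At b = 40%: 0.36 + 0.09 = 45% against 0.32 + 0.09 = 41%. Then |p0 − p1|·√n = 0.04 × 22.36 = 0.894; 1.96 × √(2 × 0.43 × 0.57) = 1.372; denominator √(0.2475 + 0.2419) = 0.700. Power = Φ(−0.683) = 25%.

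**Step 2, imperfect clinical staging.** Assume sensitivity 60% and specificity 95%. At b = 40% the share staged positive is 0.4 × 0.6 + 0.6 × 0.05 = 27%, or 135 per group. Of these, 0.24/0.27 = 89% are truly positive. Their proportions positive at surgery are 0.889 × 0.90 + 0.111 × 0.15 = 82% and 0.889 × 0.80 + 0.111 × 0.15 = 73%, giving 41% power within women staged positive. Adjusted power for all women comes from a simulated Mantel-Haenszel test stratified by staged status.

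**Step 3, range.**

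| Analysis | b = 30% | b = 40% | b = 50% |
|---|---|---|---|
| All women, unadjusted | 17% | 25% | 35% |
| All women, adjusted, staging 60%/95% | 19% | 29% | 41% |
| All women, adjusted, status known without error | 26% | 43% | 60% |
| Staged positive only, staging 60%/95% | 29% | 41% | 54% |
| Truly positive only, status known without error | 68% | 80% | 88% |

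With poorer staging (sensitivity 50%, specificity 90%) at b = 40%, both the adjusted test and the staged-positive subgroup have about 27%, so almost nothing is gained over 25%.

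**Step 4, chance imbalance.** At b = 40% the between-group difference in the entry-positive share has SD √(2 × 0.4 × 0.6/500) = 3.1 points, so a 95% range of ±6.1 points. Each point moves the surgical proportion by up to 0.90 − 0.15 = 0.75 points, so imbalance alone can shift the result by up to about ±4.6 points. The assumed treatment difference is 4 points. This variation is already part of the standard error: with no treatment effect, the unadjusted test rejects in about 5% of simulations.

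**The case against.** **The outcome is nodal status at surgery and does not claim to measure clearing.** This stands. A randomised comparison of that proportion is legitimate, and a reader who inferred bias would be wrong.

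**Low power on one of seven secondary outcomes is ordinary, and the trial is not sized on this one.** This also stands. A reader might infer that the comparison has little power in any case, but the protocol gives no nodal rates to support that. With 10% clearance of positive nodes in the control group and no new positives among entry-negatives, power at 500 v 500 is 90% if half are node-positive and clearance rises by 20 points, and 81% if 60% are node-positive and it rises by 15 points.

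**Recording palpable nodes would not rescue the comparison.** This largely stands. It is tempting to cite the 43% and 80% power at b = 40% as what baseline recording would deliver, but those figures need error-free staging. The illustration also gives entry-negatives no treatment effect. If some are occult positives whom treatment can clear, it overstates the dilution.

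**The data may be collected anyway, and the model belongs in the analysis plan.** This stands in part. Section 9 sends unlisted findings to the patient notes, section 10.2 lists an On-study Form whose content is not shown, and CRFs can be revised without a protocol amendment. It is therefore not shown that the item is absent in practice, only that the protocol does not ask for it. The choice of model alone would be no finding; the unscheduled baseline item is.

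**Conclusion.** The point holds as a modest gap in the data-collection schedule. The protocol compares nodal involvement at surgery without listing axillary status before treatment. As scheduled, baseline nodal balance cannot be checked or adjusted for, and cleared nodes cannot be told from nodes never involved. The comparison is unbiased, its type I error is unaffected, and the primary outcome is untouched.

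The precision at stake is small under realistic staging: about 17-35% power unadjusted against 19-41% adjusted, given the assumed rates and 60%/95% accuracy. The larger gains need near-perfect knowledge of entry status, and with poor staging the gain is close to nil. All these figures rest on assumed rates. The case for change rests mainly on visible balance and interpretability.

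**What to change.** In section 9, name axillary status in the screening examination. Record it on the On-study Form as clinically involved or not, with an ultrasound or cytology result where one already exists. In section 14, state that the nodal comparison will be adjusted for it, for example by logistic regression or a Mantel-Haenszel test, and that results by entry status will be reported as supportive. Show entry nodal status by arm in the baseline table.

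The cost is one form item from an examination already scheduled and one extra model; no new visit or procedure is needed. The drawback is that clinical staging is imperfect, so the report should state how entry status was determined and should not treat the staged-positive subgroup as a clean measure of nodal clearing. If the item is not added, the nodal comparison should be labelled descriptive.

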## Complete pathological response

This determined by the pathologist and defined as when all detectable tumour has disappeared.

## Local recurrence-free survival

Local recurrence-free survival is defined as time from date of trial entry to date when local recurrence is first observed and is censored at date last seen free of local recurrence in those patients who have not experienced the event.

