## 6.2 Exclusion criteria

- Bilateral breast cancer
- Evidence of distant metastases (M1)
- Patients who have received previous treatment for invasive breast cancer
- Concomitant active malignancy except for adequately treated carcinoma in situ of the uterine cervix or basal cell carcinoma of the skin
- Co-morbid disease which would preclude safe surgical treatment of the primary cancer
- Other physical or psychiatric disorder that may interfere with subject compliance, adequate informed consent or determine the causality of adverse events
- Contraindications to celecoxib: active peptic ulcer disease, renal impairment, asthma exacerbated by NSAIDs, congestive cardiac failure (NYHA II-IV\*), ischaemic heart disease, cerebrovascular disease, uncontrolled hypertension

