### **Letrozole + Celecoxib-Placebo**

Patients will receive letrozole 2.5mg, one tablet daily and celecoxib-placebo, one capsule twice daily

Treatment in all arms will continue until the day of surgery (patients should not take study medication after requirement of 'nil by mouth' for anaesthetic purposes). The surgical date should be planned in advance and will be between 16 weeks and 18 weeks from the commencement of treatment. Sufficient drug supplies will be included to cover this 2-week window.

Dose modifications of trial treatment are not permitted. Patients who are unable to tolerate the trial treatment should be withdrawn from study.

Patients whose tumours progress during the neoadjuvant phase will be withdrawn from study and treated according to local practice.

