### **Complete clinical response**

All patients require surgery. Even if no tumour is palpable or visible on ultrasound to allow an ultrasound marker then a wide local excision of the tumour site should be performed. Some centres with appropriate expertise may choose to insert clips at the same time as the day 14 biopsy in smaller tumours so that if complete clinical response occurs wide local excision can be centred on the clip.

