## 14.2 Statistical analysis

The main analysis will be carried out when all patients have completed their neoadjuvant therapy and have had their assessment of response. The main analyses comparing the objective clinical response rates will be carried out with and without adjustment for the additional randomisation; e.g. in the 500 patients receiving celecoxib vs 500 patients receiving celecoxib-placebo, objective clinical response rates will be assessed using the chi-squared test, and repeated using the Mantel-Haenszel test to allow for the adjustment of exemestane or letrozole. An additional pre-planned analysis will be the comparison of the 250 patients in each of the 4 treatment groups using one test statistic; this will be powered to detect larger differences (~13%). We do not plan to carry out multiple comparisons between the 4 treatment groups, instead we will perform one test statistic to determine if there are differences between any of the 4 treatment groups.

The secondary outcomes of survival and local control will be assessed using Kaplan-Meier survival curves, and treatments will be compared using the Log-rank test. The effect of

prognostic factors in addition to treatment will also be assessed using Cox-regression models. All analyses will be carried out on an intention-to-treat basis.

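### Local recurrence-free survival has no event for a woman whose primary progresses and is never cleared, so the local-control analysis censors her, and that censoring is informative

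*Protocol*

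**What the plan says.** The definition of local recurrence-free survival in section 14.1 fixes three things. The clock and the event are given together: "Local recurrence-free survival is defined as time from date of trial entry to date when local recurrence is first observed". Everyone else is "censored at date last seen free of local recurrence in those patients who have not experienced the event". Local progression, persistent local disease and unresected disease are not mentioned.

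Section 14.2 says that "The secondary outcomes of survival and local control will be assessed using Kaplan-Meier survival curves", compared by log-rank test, with all analyses by intention to treat. Section 14.3 adds a planned correlation of objective clinical response with local control.

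No patient is free of local disease at entry. Section 6.1 requires "Tumour, measured on U/S, as greater than 2 cm in diameter", and section 6.2 excludes "Patients who have received previous treatment for invasive breast cancer". Under section 8.1 the surgical date "will be between 16 weeks and 18 weeks from the commencement of treatment". The same section says: "Patients whose tumours progress during the neoadjuvant phase will be withdrawn from study and treated according to local practice". Section 9 (follow-up after completion of treatment) and section 10.3 nevertheless keep women who stop trial treatment early in long-term follow-up, unless they withdraw consent to it.

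**The concern.** Recurrence presupposes that the tumour was first removed. In an adjuvant trial every patient meets that condition when the clock starts. Here none does, and for about four months the local failure that can happen is progression of the primary, which the definition does not count.

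If that progression is never followed by clearance, the woman has a local failure that the local-control comparison never registers. Censoring in a Kaplan-Meier or log-rank analysis is meant to be unrelated to the risk of failure. Here she goes uncounted precisely because treatment failed. An arm with more such women would look no worse on local control. The planned correlation between response and local control would also lose some of its worst local outcomes.

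**Working it through.** The protocol gives no event rate or power for this endpoint, so there is no figure to reproduce. The check applies the rule to example patients and then shows the size under stated assumptions.

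**Rule applied to cases**

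- Patient A: local progression at week 8, never completely excised, last seen at month 36 with uncontrolled breast disease. She has no recurrence and so no event. If the censoring wording means the last date before local disease worsened, she is censored at week 8. If it means the last visit without a recorded recurrence, she is censored at month 36. The text does not choose between these.
- Patient B: excised at week 17, local recurrence at month 30. She is an event at month 30.
- Patient C: local progression at week 8, later excised, then local recurrence. The recurrence counts as an event, so the rule works for her, although her progression is ignored.

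A is a local failure under any ordinary meaning, yet is not counted on either reading.

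**Number affected (all rates assumed; none is in the protocol)**

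- Local progression on treatment, 3% to 8% of 1000 patients: 1000 × 0.03 = 30 to 1000 × 0.08 = 80.
- Never completely excised, 10% to 30% of these: 30 × 0.10 = 3 to 80 × 0.30 = 24, or 0.3% to 2.4% of all patients.
- Local recurrence after surgery by 5 years, 3% to 5%: 30 to 50.
- Share of local failures missed = never excised / (never excised + recurrences): 3/(3 + 50) = 6% to 24/(24 + 30) = 44%. The upper figure combines the highest progression rate, the highest non-excision rate and the lowest recurrence rate.

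**Effect on a comparison (illustration)**

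Take two factorial groups of 500, true post-surgical local recurrence r = 5% in both, and never-cleared progressors q1 and q2.

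- As written, censored at progression: each group shows 1 − r = 95.0%, a difference of 0 whatever q1 and q2 are.
- Counted as events: each group shows (1 − q)(1 − r), so the difference is (q2 − q1)(1 − r).

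| q1 vs q2 | Counted as events | Difference hidden |
|---|---|---|
| 0.3% vs 2.4% | 94.7% vs 92.7% | 0.021 × 0.95 = 2.0 points |
| 2% vs 5% | 93.1% vs 90.3% | 0.03 × 0.95 = 2.9 points |
| 5% vs 10% | 90.3% vs 85.5% | 0.05 × 0.95 = 4.8 points |

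The first row puts the two ends of the assumed range in opposite groups. The other two rows mostly lie above that range, so they show direction rather than likely size.

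If these women are instead censored at a late last visit, they stay in the risk set and each group shows 1 − (1 − q)r. For 2% vs 5% that is 1 − 0.98 × 0.05 = 95.10% against 1 − 0.95 × 0.05 = 95.25%. The group with more uncontrolled progression then looks 0.15 points better.

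**The case against.** The strongest reply is that the failure is recorded elsewhere. Local progression before surgery is an event in progression-free survival, timed from the same trial entry, and the calliper-based primary endpoint measures the pre-operative local effect directly. That is true, and it limits the harm. It does not repair local control, because progression-free survival also counts new tumours, and its own censoring rule refers to local recurrence.

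A second reply is that the group is small by design. Patients must have resectable disease and be fit for surgery, and section 8.3 says "All patients require surgery". This largely stands. That sentence, however, sits under complete clinical response, and progressors are handed to local practice with no statement that excision follows.

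A third is that the analysis plan may settle it. The protocol does not leave the matter open: it states start, event and censoring in full, and the stated rule gives the wrong value for these women.

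Several stronger readings are tempting but unsupported:

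- That the start date is the fault. Timing from trial entry fits the intention-to-treat plan; the event is what needs changing.
- That such a woman is scored as locally controlled, or always gets a better value than one with a late recurrence. She is censored, and only the last-visit reading produces that ordering.
- That these women are all non-responders. Section 9 assesses response at every visit and section 14.1 does not fix which visit counts, so a woman could respond and then progress.
- That the definition misses nearly half of local failures. The 44% stacks three assumed extremes.

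Section 14.2 also speaks of local control without naming local recurrence-free survival. Reading one as the other is an inference, but this is the only local time-to-event outcome that section 14.1 defines.

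**Conclusion.** The point holds in a limited form. A woman with local progression who is never cleared is censored without an event, on an ambiguous date, and that censoring depends on treatment failure. This follows from the wording alone and needs no assumed rate.

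Its size cannot be derived from the protocol. On the assumed rates it concerns 3 to 24 of 1000 patients across all arms, and only an imbalance between groups within that number would affect a treatment comparison. The endpoint is secondary, carries no power claim, and leaves the primary response analysis untouched. The wording should still be changed, because the change is cheap and the current rule can hide the local failure most specific to pre-operative treatment.

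**What to change.** In section 14.1, keep the clock at trial entry and define the event as local failure, the earlier of:

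1. documented local progression of the primary before surgery, dated when first observed, whatever treatment follows; and
2. local recurrence after surgery.

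Censor at the date last seen without either event. Report the current recurrence-only version as a sensitivity analysis, with its censoring date for never-cleared progressors stated.

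Dating the event at progression regardless of later surgery matters. If it depended on whether excision followed, status at week 8 would turn on the future, and completeness of excision would be needed, which the protocol does not clearly collect.

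The definition must also name one progression criterion. Section 9 uses an increase of more than 30%, Appendix 4 at least 20%, and section 14.1 gives no threshold; these passages must be reconciled.

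The cost is wording. Section 9 already asks for full details of progression on the case report forms, and section 10.2 lists post-operative and relapse forms. The downside is small: progressors later excised successfully count as local failures (on the assumed rates 30 to 80 progressors in all, against 3 to 24 never cleared), and the result is less comparable with adjuvant trials. The sensitivity analysis shows the effect of both.
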